8.1. Definitions

Serious adverse events include persistent hypotension, persistently prolonged QTc, ileus, anaphylaxis and death.

#UTHealth Houston

8.2. Collecting, Recording and Reporting of Adverse Events

The principal investigator will be responsible for accurate documentation, investigation and followup as well as timely reporting of the following:

- 1- Any adverse event at the study site which in the opinion of the principal investigatoris both unexpected and related and places subjects or others at risk ofharm
- 2 Information that indicates a change to the risks or potential benefits of theresearch
- 3- An interim analysis or safety monitoring report indicates that frequency or magnitude of harms or benefits may be different than initially presented to the IRB
- 4 A paper is published from another study that shows that the risks or potential benefits of the research may be different than initially presented to the IRB
- 5 A breach of confidentiality
- 6 Change in FDA labelling or withdrawal from marketing of a drug, device or biologic used in a research protocol
- 7- Change to the protocol taken without prior IRB review to eliminate an apparent immediate hazard to a research participant
- 8 Incarceration of a participant in a protocol not approved to enroll prisoners
- 9- Event that requires prompt reporting to the sponsor
- 10- Sponsor imposed suspension
- 11- Complaint by a participant when the complaint indicates unexpected risks or cannot be resolved by the research team
- 12- Protocol deviation meaning an accidental or unintentional change to IRB approved protocol) that harmed participants or others or that indicates that participants or others may be at increased risk of harm
- 13- Unanticipated adverse device effect

Nursing staff and physicians will be notified to look out for the above. Any identified adverse event will be reported to the study PI who will discuss and inform the study coordinator aboutit.

The Principal investigator shall make a judgement about the expectedness of a problem. If the problem is an adverse event, the investigator shall make a judgement about the causality of the adverse event with respect to study intervention. The Principal investigator shall also evaluate whether protocol consent forms are needed.

The Principal investigator shall state whether the problem is expected or unexpected.

For adverse events the Principal Investigator shall evaluate the event and assess causality. He shall reveal evidence or arguments to suggest causal relationship

The Principal Investigator shall report the reportable events described above to CPHS via iRIS as follow: All problems involving local deaths shall be reported immediately, within 24 hours after first knowledge by the investigator. All other problems shall be reported as soon as possible but not later than 7 calendar days after first knowledge by the investigator.

Safety Monitoring Plan

The research team will meet once every 3 months to review adverse events, protocol deviations and other problems encountered. We will work with IRB to create a data and safety monitoring board. A data safety monitoring board will be created and will meet once every quarter to assess study conduct and progress and determine continuity of the study.

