2.3. Secondary Objectives

To assess the safety of methadone administration in critically ill patients while in the hospital.

To determine hospital length of stay from the time of enrollment to the time of discharge

2.4. Potential Risks and Benefits:

a. End Points – Efficacy

The study might show the efficacy and potency of methadone in decreasing the length of stay in ICU and duration of mechanically intubation in critically ill patients.

b. End Points - Safety

Adverse events that could be anticipated during the study include signs of opioid withdrawal, elevated liver enzymes, ileus, hypotension and QTC prolongation. Adverse events will be reported in the adverse events registry.

The only two adult studies reported on the use of methadone to wean opioids on mechanical ventilation showed that the much-anticipated risk of QTC prolongation was similar in both patients who received methadone and those that did not receive methadone as shown in the study by Wanzuita et al and Al-Qadheeb et al. [5] Methadone was well tolerated in both studies.

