8. SAFETY MEASUREMENTS

Any adverse events encountered will be documented in the patients' chart once it is noted. These include QTc >500, high grade arrhythmias such as ventricular tachycardia, hypotension and elevated Liver function testing more than 2.5 times the upper limit of normal.

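### Anticipated methadone harms that the protocol itself lists as serious have no defined expedited report and no defined route to the DSMB

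*Combined protocol and SAP*

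**What the plan says.** Section 8.2 makes the principal investigator responsible for reporting 13 kinds of problem. Item 1 is the general rule for a single adverse event: in that investigator's opinion it must be "both unexpected and related and places subjects or others at risk" of harm. Two other items work at the level of overall risk. Item 2 covers "Information that indicates a change to the risks or potential benefits of" the research, and item 3 applies when an interim analysis or "safety monitoring report indicates that frequency or magnitude of harms or benefits may be different than initially presented to the IRB". Item 12 covers harmful protocol deviations.

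Reportable problems go to CPHS (which I take to be the IRB), within 24 hours if they involve a local death and within 7 calendar days otherwise. Internally, "Any identified adverse event will be reported to the study PI who will discuss and inform the study coordinator".

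The two lists that matter here are in sections 2.4b and 8.1:
- Section 2.4b: "Adverse events that could be anticipated during the study include signs of opioid withdrawal, elevated liver enzymes, ileus, hypotension and QTC prolongation".
- Section 8.1: "Serious adverse events include persistent hypotension, persistently prolonged QTc, ileus, anaphylaxis and death".

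The Safety Monitoring Plan within 8.2 has the research team review adverse events every 3 months. The DSMB, still to be created, "will meet once every quarter to assess study conduct and progress" and to decide whether the trial continues. Section 10.2 states that no safety analysis is planned. It provides one interim analysis at 40 randomised patients, reported to the DSMB.

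**The concern.** The definition of a serious event in 8.1 is not used by any reporting step: neither the 13 items nor the two clocks refer to seriousness. What decides whether a single event leaves the study team is expectedness and relatedness. The harms most likely to matter with methadone are the ones the protocol says it expects, so a serious instance of one of them would ordinarily drop out at item 1.

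That would be acceptable if the board saw those events by another path. But the plan names no adverse-event listing, by arm or otherwise, among the board's inputs. Assessing methadone safety is a stated secondary objective (2.3), and the board is asked to decide on continuation. It could be asked to do so without counts, by randomised arm, of the harms the protocol anticipates.

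**Working it through.** The plan gives no figure on this point to reproduce. The check is to set the reporting routes side by side and ask whether each would carry one serious but expected event, such as an ileus, out of the study team.

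| Route | Carries one expected serious event? | Goes to |
|---|---|---|
| 8.2 item 1 | No, once judged expected | IRB |
| 8.2 items 2 and 3 | Only as part of a changed overall risk | IRB |
| 8.2 item 9 (events needing prompt report to the sponsor) | Not stated; no section says which events these are | IRB |
| 8.2 item 12 | Only if a protocol deviation was involved | IRB |
| 8.2 death clock | Deaths only; scope unclear, since it governs the reportable items listed above it | IRB |
| 8.2 internal notification | Yes | Principal investigator, coordinator |
| Three-monthly review | Yes | Research team |
| 2.4b adverse events registry | Yes | Recipient not stated |
| Quarterly board meeting | Not stated | DSMB |
| 10.2 interim at 40 patients | Not stated | DSMB |

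**Matching the lists.** Three of the five entries in 8.1 (hypotension, QTc, ileus) name conditions that 2.4b calls anticipated; 8.1 adds persistence for the first two. Anaphylaxis and death are not in 2.4b.

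**Can the aggregate routes do the work?** Item 3 needs an interim analysis or a safety report to show a changed frequency of harm. Section 10.2 rules out a safety analysis and does not say what the single interim contains. QTc prolongation and mortality could appear there, because 2.5b makes them secondary outcomes. However, 2.5b defines the QTc outcome only after methadone is given, and Appendix 6 records mean QTc while on methadone. Section 6 has QTc documented daily, so control values may exist, but no comparison with control is specified.

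**Scale.** Inputs: 80 patients (10.1), 1:1 allocation (4.1), 2 years (5.1).
- Accrual between board meetings, assuming it is even over the full 2 years: 80 / 8 quarters = 10 patients, or 5 per arm.
- Event rates are not in the documents, so I assume p = 5%, 10% or 20% for one anticipated harm. Expected events = n × p; chance of at least one = 1 − (1 − p)^n.

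| p | n = 40 (full methadone arm): expected; chance of at least one | n = 20 (methadone half of the interim): expected; chance of at least one |
|---|---|---|
| 5% | 2; 87.1% | 1; 64.2% |
| 10% | 4; 98.5% | 2; 87.8% |
| 20% | 8; over 99.9% | 4; 98.8% |

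Under these assumptions such events are likely to occur. If each is judged expected, item 1 requires a report of none of them.

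**The case against.** A reader might infer that the serious list triggers nothing and that anticipated harms never have to reach the board or the IRB. The documents do not support that. Items 2, 3 and 12 have no unexpectedness condition, local deaths have a 24-hour clock, and an interim report goes to the DSMB.

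Nor can one say that anticipated events cannot qualify under item 1. The investigator judges expectedness event by event, nothing makes 2.4b the reference for it, and a persistent form could be judged worse than what was anticipated.

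It is also tempting to say that relatedness is judged with knowledge of the arm. Sections 6.1 and 7.5 leave treating physicians and nurses unblinded but blind the investigators who evaluate outcomes. The principal investigator's status when assigning causality is not stated.

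The 8.1 list is worded as inclusive, so the absence of "high grade arrhythmias such as ventricular tachycardia", which section 8 names as an adverse event, does not prove exclusion. The same holds for respiratory depression, which the label in Appendix 3 places first among the major hazards. Neither is in 2.4b, so either could meet item 1 if judged unexpected and related.

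Finally, the board's remit includes continuation, section 3.5 lets it recommend stopping, and its inputs could still be settled when it is formed.

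All of this narrows the point. It does not supply a written route by which a single serious, expected event, or a count of such events by arm, reaches the board.

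**Conclusion.** The point holds in this form. Individual anticipated harms, including persistent hypotension, persistent QTc prolongation and ileus from the serious list, would ordinarily be judged expected. They then have no defined expedited report and no defined route to the DSMB. Only a change in overall harm is reportable, and the plan specifies no by-arm analysis that would detect one.

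This rests on two readings: that an event the protocol calls anticipated would normally be judged expected, and that inputs not named for the board are not guaranteed to it. The size cannot be fixed from the documents. The 2 to 8 events are illustrative, and the 10 patients per quarter describe accrual, not unreported harm. I class this as a cheap improvement to safety oversight; it does not show that harm would go unseen.

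**What to change.** 1. In 8.2 and the Safety Monitoring Plan, state that every serious adverse event in either arm, whatever its expectedness or relatedness, goes to the DSMB on the clocks already in 8.2: 24 hours for deaths, 7 calendar days otherwise.
2. State that cumulative counts of adverse and serious adverse events by randomised arm go to each quarterly DSMB meeting. Coded arm labels would fit the blinded statistician in 10.2.
3. In 10.2, replace the statement that there will be no safety analysis with this by-arm tabulation.
4. Reconcile the 8.1 list with section 8 on ventricular tachycardia and with the appended label on respiratory depression. Do not add a prolonged-stay criterion: entry already requires more than 72 hours of ventilation and a failed breathing trial (3.3), so it would capture many participants.
5. Keep the unexpected-and-related rule for individual IRB reports.

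The cost is protocol wording and a listing for meetings already scheduled. Appendix 6 has a single adverse-event field, so event type, seriousness and date may need adding unless the registry in 2.4b already holds them. The downside is somewhat more reports in a population where serious events are frequent.

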9. DATA ANALYSIS

9.1. Data Quality Assurance

#UTHealth Houston

After physician or advanced care practitioner entry of information into patient database, research coordinator will verify information for accuracy and correctness. There will be no plans to have ongoing third-party monitoring.

9.2. Data Entry and Storage

Data will be entered electronically on REDCAPs data base. All information will be stored on UTHealth computers.

10. SAMPLE SIZE AND STATISTICAL METHODS

10.1. Determination of Sample Size

Based on the assumptions of successful extubation by day 5 of 50% of patients in the methadone group and 20% of patients in the Non Methadone group and using a two tailed alpha level of 5%, a power of 80% our sample size calculation comparing proportions of two groups yielded 76. A 5% fall out as correction factor was 4 leaving us with a sample size of 80 patients.

10.2. Statistical and Analytical Plans

Methadone when used at appropriate doses is considered safe and is an FDA approved medication. We will not be performing safety analysis. We will perform interim analysis after randomizing up to 50%(40) patients. Categorial variable will be compared using the student Chisquared test and continuous variables will be compared using the T-test. Interim analysis will be performed by an independent statistician blinded for the treatment allocation. The statistician will report to the data safety and monitoring committee. The DSMB will discuss the results of the interim analysis with the statistician and a steering committee and in a joint meeting will decide on continuation of the trial.

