2.5 Outcomes

a. Primary

Proportion of patients on methadone that get extubated by day number 5 from the date of intubation

b. Secondary

Proportion of patients that develop prolonged QTC after administration of methadone. Others will be ICU length of stay, ICU mortality, hospital length of stay and hospital mortality.

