3.4. Exclusion Criteria

All subjects meeting any of the exclusion criteria at baseline will be excluded from participation.

- 1. Patients with history of opioid drug abuse
- 2. Patients receiving schedule II narcotics on a chronic basis for longer than 6 months prior to ICU admission or on other analgesic infusions other than Fentanyl or Hydromorphone
- 3. Patients with cervical spinal cord injury or neuromuscular disease
- 4. Patients with end stage liver disease at ICU admission (ie, International normalized ratio ≥2and not taking warfarin and/or a total serum bilirubin ≥1.5 times above normal limits
- 5. Patients with prolonged QTc interval ≥500
- 6. Patients with prior history of cardiac conduction defects or suddendeath
- 7. Patients with QTc increase of ≥60 milliseconds above the value of prior EKGs measured during current ICU admission
- 8. Patients with more than 5 days on IV analgesia
- 9. Patients intubated for more than 30 days
- 10. Patients without feeding tubes
- 11. Patients not receiving enteral feeding
- 12. Exclusion of patients in a comatose state
- 13. Exclusion of patients in Status Epilepticus
- 14. Exclusion of post-operative patients

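### Section 10.2 rules out any safety analysis although safety is a secondary objective and prolonged QTc a secondary outcome; the QTc outcome is undefined and does not match the printed form

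*Combined protocol and SAP*

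**What the plan says.** Section 10.2 gives as its reason that methadone at suitable doses is regarded as safe and is approved, and then states "We will not be performing safety analysis". No word such as formal or interim limits the sentence.

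Section 2.3 has the secondary objective "To assess the safety of methadone administration in critically ill patients while in the hospital". Section 2.5 has the secondary outcome "Proportion of patients that develop prolonged QTC after administration of methadone".

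QTc appears elsewhere in three forms:

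- Section 3.4 (exclusions): "Patients with prolonged QTc interval ≥500" and "Patients with QTc increase of ≥60 milliseconds above the value of prior EKGs measured during current ICU admission".
- Section 8 (adverse events): "These include QTc >500".
- Section 8.1 (serious adverse events): "Serious adverse events include persistent hypotension, persistently prolonged QTc, ileus, anaphylaxis and death", with no figure for QTc.

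Section 6 plans a daily QTc from the patient monitors, entered on the data collection tool, and does not limit this to one arm. It names Appendix 6 as the sheet completed before transfer to REDCap. The printed Appendix 6 has one QTc field, the mean while on methadone. Under section 4.2 a patient's participation can end at extubation.

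**The concern.** The statements in 2.3, 2.5 and 10.2 cannot all be followed. A team that reads 10.2 literally has grounds to omit the safety objective. A team that reports QTc anyway can choose the definition after seeing the data, because 2.5 gives no cut-off and does not say whether a 60 ms rise counts.

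The comparator is also unstated. The primary outcome, "Proportion of patients on methadone that get extubated by day number 5 from the date of intubation", is worded for methadone patients in the same way, and section 10.1 sizes the trial on a comparison of the two arms. A between-arm comparison is therefore probably meant for QTc too, but the plan does not say so.

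The data route does not fit either: the plan is for daily values and the form asks for a mean. Finally, the trial expects earlier extubation on methadone (50% against 20% by day 5). If QTc observation stops at extubation, the methadone arm has fewer days on which an event can be seen, so a bare proportion would tend to favour it.

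**Working it through.** **1. The text.** Safety is an objective (2.3), QTc is an outcome (2.5), and no safety analysis is planned (10.2). No arithmetic is needed here; the three statements conflict.

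**2. Plan's own figure, used only for the arm size.** 76/0.95 = 80 patients; 1:1 allocation gives 40 per arm.

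**3. Can a mean give the outcome?** Assumed five-day QTc values, in ms:

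- Four days at 440 and one at 520: (4 × 440 + 520)/5 = 456.
- Four days at 480 and one at 520: (4 × 480 + 520)/5 = 488.
- Five days at 480: mean 480, no day above 500.

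A patient with an event can have a mean of 456, below the 480 of a patient without one. The mean does not determine the outcome. A control patient has no mean on methadone at all.

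**4. Unequal observation.** The documents give no daily risks and no days observed; all are assumed. With daily risk p over d days, the proportion with an event is 1 − (1 − p)^d. Take the same p in both arms, with 3 days on methadone and 8 on control:

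| p | methadone | control | gap |
|---|---|---|---|
| 1% | 2.97% | 7.73% | 4.8 points |
| 2% | 5.88% | 14.92% | 9.0 points |
| 3% | 8.73% | 21.63% | 12.9 points |

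At 2% the expected counts are 0.0588 × 40 = 2.4 and 0.1492 × 40 = 6.0. With 4 against 6 days at 2%, the proportions are 7.8% and 11.4%, a gap of 3.7 points.

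In the other direction, the methadone daily risk over 3 days that would match 14.92% is 1 − (1 − 0.1492)^(1/3) = 5.2%. That is 2.6 times the control risk, with no difference in the proportions. For 4 against 6 days the ratio is 1.5.

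**5. Does a per-day rate repair this?** Only if the daily risk is constant. At p = 2%, days at risk to first event per 40 patients are 117.6 and 298.5, so 2.35/117.6 = 5.97/298.5 = 2.0 per 100 days in both arms. Now assume identical risks that rise: 0.5%, 1% and 2% on days 1 to 3, then 3% a day.

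- 3 days: first events per patient 0.005 + 0.995 × 0.01 + 0.985 × 0.02 = 0.0347; days at risk 1 + 0.995 + 0.985 = 2.98; rate 1.2 per 100 days.
- 8 days: first events 0.0347 + 0.9653 × (1 − 0.97^5) = 0.171; days at risk 2.98 + 0.9653 × (1 + 0.97 + 0.97² + 0.97³ + 0.97⁴) = 7.53; rate 2.3 per 100 days.

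Equal risks again look unequal. The label in Appendix 3 says methadone takes at least 3 to 5 days to reach steady state, so a risk that changes over time is plausible.

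**6. Precision.** Assumed counts 6/40 and 2/40. Wilson 95% limits are 7.1% to 29.1% and 1.4% to 16.5%. The Newcombe limits for the 10-point difference are:

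- lower: 0.10 − √((0.150 − 0.071)² + (0.165 − 0.050)²) = −0.040
- upper: 0.10 + √((0.291 − 0.150)² + (0.050 − 0.014)²) = 0.245

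Expected counts in the event cells are 8/2 = 4 each. The comparison is descriptive.

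**The case against.** A reader might infer that the safety objective and the QTc outcome are certain to go unreported. The documents do not support that. Two sentences after the disputed one, 10.2 says categorical variables will be compared by chi-squared, and the QTc proportion is categorical. Section 2.4b sends adverse events to a registry. Section 8 would have a QTc above 500 charted. The research team and the DSMB review the study every quarter, and 8.2 foresees a safety monitoring report. This weakens the contradiction but does not settle it. The chi-squared sentence stands between two sentences on the interim analysis and defines neither the outcome nor the comparator. Monitoring is not a planned summary by arm.

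A reader might also infer that daily QTc values will be lost, or that a day above 500 would vanish from the record. Neither follows. Such a day is hidden in the mean, but it may be charted, and Appendix 6 has an adverse-event line. The REDCap build is not shown. As extracted, the printed sheet also lacks an extubation date, death and hospital stay, so it may not be the full record. What stands is a mismatch between section 6 and the printed form.

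Fewer QTc days on methadone may partly be a real benefit, since methadone stops at extubation. That is fair: the proportion answers a question about the whole strategy. It does not answer whether risk per day of exposure is raised, so days observed should be shown beside it.

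Forty patients per arm are too few for firm safety conclusions. That supports descriptive reporting, not omission.

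**Conclusion.** The point holds as contradictory wording, an undefined outcome and a form that does not match the collection plan. Confidence in these is high because they rest on the text alone. The plan should be changed, although the primary comparison is unaffected.

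The size of any distortion is not known. The gaps of 3.7 to 12.9 points rest wholly on assumed daily risks (1% to 3%) and assumed days observed (3 against 8, or 4 against 6). Only the direction follows from the design, and only if QTc observation stops at extubation and extubation is in fact earlier on methadone.

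One might conclude that a per-day event rate would solve the problem. It would not do so in general, as the rising-risk example shows, so such a rate is supportive only.

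**What to change.** 1. In 10.2, replace the sentence with: *Safety will be reported descriptively by randomised arm: adverse events, and the QTc outcome with the risk difference and 95% Newcombe CI.*
2. In 2.5, define the QTc outcome, for analysis only, in all randomised patients of both arms as any daily monitor QTc above 500 ms after randomisation. This is the protocol's own adverse-event figure. Section 3.4 already excludes a QTc of 500 or more at baseline, so no randomised patient need be left out. Reconcile the QTc wording in 2.5, 3.4, 8 and 8.1.
3. In Appendix 6, replace the mean with the daily monitor values for both arms, or with the maximum, the date first above 500 and the number of QTc days.
4. Report QTc days observed and first events by study day in each arm beside the proportion. Label any per-day rate as supportive, because it assumes a constant daily risk.

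The cost is some wording, a few form fields and a small data-entry burden for about 40 control patients, using monitor values that section 6 already plans. The estimate stays imprecise and descriptive. No eligibility, dose or treatment rule changes.

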4.2 Interventions

Pre-intervention period (1 month)

The objective of this period is to standardize the process to improve familiarity to the investigators. Study procedures will be presented to the nurses by oral presentations, printed material, and by email. The information will include detailed explanation of the process of tapering methadone and weaning patients off opiates as stipulated in the study. It will also elaborate more on the process of managing patients that develop clinical opiate withdrawal symptoms.

Intervention period

Following randomization patients will be assigned to the MG or the NG group. For patients randomized to the MG a "non-formulary medication" order will be placed in the electronic medical record to alert nurses to follow the protocol for patients started on Methadone. For those in the NG group usual hospital protocol of weaning opioids will be followed.

The study is completed for each patient once extubated or discharged from ICU, death, comfort care measures, or after 30 days of participation in the study.

We will collect data regarding participants demographic characteristics, comorbidities, main admission diagnosis, use of mechanical ventilation and vasopressors, ICU and hospital LOS, ICU and hospital mortality. Vital signs, focused general examination, LFTs, with normal ICU standard of care will done. However, EKG will be done at baseline and on day 30 if patient is still on methadone. LFTs are only done at baseline. The duration of use of the medication is not expected to cause an increase in LFTs. The listed labs are the only additional labs other than what is usually ordered for standard care in ICU. The information will be collected by reviewing medical records and will be recorded in electronic form only, using REDCap.

#UTHealth Houston

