Bone or Joint aches If patient was having pain previously, only the additional component attributed to opiates withdrawal is scored O not present mild diffuse discomfort patient reports severe diffuse aching of joints/muscles patient is rubbing joints or muscles and is unable to sit still because of discomfort	Gooseflesh skin 0 skin is smooth 3 piloerrection of skin can be felt or hairs standing up on arms 5 prominent piloerrection			
Runny nose or tearing Not accounted for by cold symptoms or allergies 0 not present 1 nasal stuffiness or unusually moist eyes 2 nose running or tearing 4 nose constantly running or tears streaming down cheeks	Total Score The total score is the sum of all 11 items Initials of person completing assessment:			

Score: 5-12 = mild; 13-24 = moderate; 25-36 = moderately severe; more than 36 = severe withdrawal This version may be copied and used clinically.

Journal of Psychoactive Drugs

[figure not shown]
Volume 35 (2), April - June 2003

Source: Wesson, D. R., & Ling, W. (2003). The Clinical Opiate Withdrawal Scale (COWS). J Psychoactive Drugs, 35(2), 253–9.

Appendix 5

Protocol Flow

Appendix 6

#UTHealth Houston

Data Collection Tool

Patient Identification Code (MRN):

Baseline Characteristics Age (years) Sex		
Sex		
Race		
Weight (Kg)		
Duration on ventilator at time of		
randomization (Hours)		
	Pneumonia = 1	
, , ,	Aspiration = 2	
	Non-Pulmonary Sepsis = 3	
	COPD Exacerbation = 4	
	Other Causes = 5	
Assessments and Measurements	Other Causes - 5	
APACHE II Score		
Total SOFA Score		
Tidal Volume ml/kg of predicted		
body weight		
Peep at time of enrollment (cm H2O)		
PaO2: FIO2 ratio (mmHg)		
FiO2 at time of enrollment		
Duration on mechanical ventilation		
before start of weaning(hours)		
Last recorded Ph prior to enrollment		
Duration in ICU stay after enrollment		
(Hours)		
Mean QTc while on Methadone		
Clinical Opiate Withdrawal Scale		
(COWS) after extubation		
Adverse Event		
Medication Parameters		
Fentanyl Initial Dose (mcg/hour)		
Fentanyl accumulated dose(mcg)		
Days on Fentanyl before start of		
weaning		
Hydromorphone initial Dose		
(mg/hour)		
Hydromorphone accumulated		
dose(mg)		
Days on Hydromorphone before		
start of weaning		
Dexmedetomidine accumulated		
dose(mcg)		
Midazolam accumulated dose(mg)		
Propofol accumulated dose (mg)		
Ketamine accumulated dose (mg)

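### Section 10.2 rules out a safety analysis, against the plan's own safety objective and QTc outcome, and no by-arm summary of QTc or non-fatal adverse events is stated

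*Combined protocol and SAP*

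**What the plan says.** Section 10.2 gives as its reason that methadone at appropriate doses is regarded as safe and is an approved drug. It then states: "We will not be performing safety analysis. We will perform interim analysis after randomizing up to 50%(40) patients". A general sentence follows, naming a chi-squared test for categorical variables and a t-test for continuous ones. It names no safety variable.

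Other sections point the other way:

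- **Section 2.3** lists as a secondary objective: "To assess the safety of methadone administration in critically ill patients while in the hospital".
- **Section 2.5** opens its secondary outcomes with: "Proportion of patients that develop prolonged QTC after administration of methadone". ICU and hospital mortality and length of stay follow.
- **Section 2.4** says: "Adverse events that could be anticipated during the study include signs of opioid withdrawal, elevated liver enzymes, ileus, hypotension and QTC prolongation". It sends adverse events to a registry.
- **Sections 8 and 8.1** list the adverse and serious adverse events to be charted, including QTc >500.
- **Section 8.2, item 3** makes reportable any interim analysis or safety report showing that harms differ in frequency from what the IRB was told. It therefore presupposes such a report.

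On measurement, section 4.2 says: "EKG will be done at baseline and on day 30 if patient is still on methadone", and of liver tests: "LFTs are only done at baseline". The QTc line in Appendix 6 reads "Mean QTc while on Methadone". Section 6 says QTc will be taken from monitors and recorded daily, with no mention of arm.

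**The concern.** A statistician who follows section 10.2 to the letter would produce no analysis for a stated objective.

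QTc is where this matters most. Section 2.4 takes reassurance from earlier studies in which "the much-anticipated risk of QTC prolongation was similar in both patients who received methadone and those that did not receive methadone". That is a between-group comparison. This trial randomises a control group that could supply the same comparison, but nowhere says that it will be made. A proportion from the methadone arm alone cannot separate a drug effect from the background of QTc prolongation in intensive care. The label in Appendix 3 carries a boxed warning on life-threatening QT prolongation, so the stated reason for omitting the analysis does not settle the question.

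The form matters too. If daily QTc is not captured prospectively in control patients, it may be hard to recover later.

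**Working it through.** The point is mainly textual, so the first three steps set the sections side by side. The last uses arithmetic to show what the remedy can deliver.

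**1. What section 10.2 leaves unanalysed.** Section 2.3 has two secondary objectives, safety and hospital length of stay; the first is excluded. Section 2.5 has five secondary outcomes: prolonged QTc, ICU stay, ICU mortality, hospital stay and hospital mortality. The last four are not safety analyses in the plan's own terms, and the general test sentence can cover them. Prolonged QTc is the one that conflicts.

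**2. Which harms have a by-arm comparison.** Section 8.1 lists five kinds of serious event: persistent hypotension, persistently prolonged QTc, ileus, anaphylaxis and death. Death is covered through the mortality outcomes. The other four are not named in any comparison. Nor are the five anticipated harms in section 2.4.

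**3. What is recorded for QTc.**

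| Source | Wording applies to |
|---|---|
| Section 2.5, outcome | after methadone |
| Appendix 6, only QTc line | while on methadone, as a mean |
| Section 4.2, ECG after baseline | day 30, if still on methadone |
| Section 6, daily monitor QTc | no arm restriction |
| Section 8, QTc >500 as adverse event | no arm restriction |

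Control readings may therefore exist, but the printed sheet has no QTc line for them. A mean is also a poor match for a threshold of 500. With assumed values of one reading at 520 and the rest at 440, the mean is (2×440 + 520)/3 = 467 over 3 days, (4×440 + 520)/5 = 456 over 5 days and (7×440 + 520)/8 = 450 over 8 days.

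**4. Precision available.** Section 10.1 assumes 50% v 20% extubated by day 5, two-sided 5% alpha and 80% power, and reports 76 patients. The pooled formula gives, per arm,

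n = [1.96√(2×0.35×0.65) + 0.84√(0.5×0.5 + 0.2×0.8)]² / 0.30² = (1.322 + 0.539)² / 0.09 = 38.5, so 39.

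That is 78 in total, within two of the plan's figure. Adding the plan's 4 for dropout to its 76 gives 80, or 40 per arm at 1:1. This size was set for extubation, not for harm. At 40 per arm:

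- No events in 40: exact two-sided 95% upper limit = 1 − 0.025^(1/40) = 8.8%.
- 6 v 2 events (illustrative): 15% − 5% = 10 points, Newcombe 95% CI −4.0 to 24.5.
- The documents give no QTc event rate. For assumed control rates of 5%, 10%, 15% and 20%, 80% power needs increases of about 23, 26, 28 and 29 points.

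A formal safety test would have little power. A table of counts by arm with intervals is the realistic aim.

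**The case against.** The best defence is that the sentence in section 10.2 sits beside the interim plan and may have meant no *interim* safety analysis. The text does not say so, and no final safety analysis is described elsewhere. If that was the intent, a correction is still needed.

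Several stronger readings are tempting and should be resisted:

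- **That no harm at all is compared between arms.** ICU and hospital mortality are secondary outcomes, section 1.2 commits to comparing outcomes between arms, and a test for categorical variables is named. Death is covered.
- **That methadone-only wording proves no QTc comparison was intended.** The primary outcome in section 2.5 is also worded for methadone patients, yet section 10.1 sizes it as a two-arm comparison. This may be drafting style. What stands is that the comparison is unstated and the form does not support it.
- **That the safety objective would rest on methadone-only QTc means.** The stated outcome is a proportion. Section 8 requires QTc >500 to be charted, and Appendix 6 has an adverse event line that is not limited by arm. The printed sheet also shows no mortality field, although section 4.2 says mortality is collected, so it is not shown to be the whole dataset.
- **That earlier extubation would make methadone look falsely safe.** Participation can end at extubation, so observation time may differ between arms. But the documents give no harm rates, withdrawal is followed after extubation (section 5.1) and hospital mortality runs on to discharge. The size of any distortion cannot be derived from the plan.
- **That the DSMB will not see harms by arm.** The protocol is silent about a board not yet formed, and a charter could fill this gap. A charter would not correct section 10.2, the outcome wording or the form.

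**Conclusion.** The concern holds in a limited form. Section 10.2 contradicts sections 2.3 and 2.5, and nothing else in the document removes the contradiction. Its extent is one of two secondary objectives, one of five secondary outcomes, and the lack of any stated by-arm summary for QTc and non-fatal adverse events. Mortality is outside the criticism.

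The conclusion rests on the text alone and needs no assumed event rate. The QTc values and event counts in the working are illustrations, not predictions of harm. The change should be made, and it is small. The efficacy analysis is not affected.

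**What to change.** 1. **Section 10.2.** Replace the sentence excluding safety analysis with a descriptive summary by arm. List the number of patients with each of: QTc >500, high-grade arrhythmia, hypotension, ileus, anaphylaxis, liver tests above 2.5 times the upper limit, opioid withdrawal (COWS) and death. Because protocol liver tests are baseline only, count liver events where routine care measured them and give that denominator. Show observation time per arm alongside, since participation can end at extubation (section 4.2). Do not require a rate per day for every event: it does not suit withdrawal scored after extubation, or death in hospital.
2. **Section 2.5 and Appendix 6.** Define the QTc outcome as the proportion with QTc >500 in each arm. Change the form line to the daily, or maximum, monitor QTc in both arms, to match section 6.
3. **Safety Monitoring Plan (section 8.2).** State that the planned DSMB receives this table.

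The cost is a short amendment, a form change and a little more data entry. QTc already comes from monitors and the section 8 events are already charted, so the summary needs no additional patients. The limitation is imprecision at about 40 per arm, so the text should say that the summary is descriptive and that an absence of events is not evidence of safety.
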